DSM-V	Diagnostic and Statistical Manual of Mental Health – Fifth Edition
eCRF	electronic case report form
FDA	Food and Drug Administration
ICBT	Ishihara Color Blindness Test
ICF	informed consent form
IRB	institutional review board
IRS	Impairment Rating Scale
KBIT	Kaufman Brief Intelligence Test
LD	learning disability
MAOI	monoamine oxidase inhibitor
MFaCTs	Mathematics Fluency and Calculation Tests
MINI-KID	MINI International Neuropsychiatric Interview for Children and Adolescents
OTC	over the counter
PI	principal investigator
ROC	receiver operator curve
SAP	statistical analysis plan
SSRI	selective serotonin reuptake inhibitor
ToSREC	Test of Silent Reading Efficiency and Comprehension
TOVA-9	Test of Variables of Attention – version 9
UADE	unanticipated adverse device effect

1 PROTOCOL SUMMARY

1.1 SYNOPSIS

Title:	Software Treatment for Actively Reducing the Severity of ADHD as Adjunctive Treatment to Stimulant
Phase:	Post Registration Follow Up Trial
Description of Study Intervention & Symptom Tracking:	
Intervention: AKL-T01 is digital therapeutic software for the neuromodulatory treatment of attention and inhibitory control deficits in pediatric patients with attention deficit hyperactivity disorder. AKL-T01 is an investigational medical device known as Software as a Medical Device (SaMD).
 
Symptom Tracking: AKL-X01 (Fengo) is a mobile application (app) that provides a convenience service to caretakers to capture their routine observations of their child's ADHD symptoms and behaviors in a structured format. AKL-X01 (Fengo) captures symptoms data and provides simple graphical displays; it is not an investigational medical device.

Study Description:	
The study aims to enroll (203) participants, with a confirmed diagnosis of ADHD, at approximately 15 sites and will be divided between 2 cohorts; (130) participants will be enrolled in Cohort 1, and (73) participants will be enrolled in Cohort 2.
 
Cohort 1, the primary cohort, will have been stable (adherence to a prescribed medication schedule) on a stimulant medication, but are inadequately managed by the stimulant (in the opinion of the investigator). The stimulant is managed by their own physician for at least 30 days before baseline. This is the "stimulant cohort."
 
Cohort 2, the secondary cohort will have been stable without any stimulant medication for at least 30 days before the baseline. This is the "no stimulant" cohort.
 
For both cohorts, at least 7 and up to 30 days before baseline, participants' caretakers will

begin using AKL-X01 (Fengo) to track their participants' symptoms and behaviors.

During Treatment Phase 1 (Days 1 through 28) participants in Cohort 1 (stimulant) will continue to receive their current stimulant plus the addition of AKL-T01. Participants in Cohort 2 (no stimulant) will only receive AKL-T01. For both cohorts, during this time the caretakers will monitor their child's symptoms daily with AKL-X01.

During the 1-Month Break (Days 29 through 56) between AKL-T01 treatment phases, participants in Cohort 1 (stimulant) will continue to receive their current stimulant. In both cohorts, AKL-T01 will be suspended during this time. For both cohorts, during this time caretakers will continue to monitor their child's symptoms daily with AKL-X01.

During Treatment Phase 2 (Days 57 through 84), participants in Cohort 1 (stimulant) will continue to receive their current stimulant plus the addition of AKL-T01. Participants in Cohort 2 (no stimulant) will just receive AKL-T01. For both cohorts, during this time the caretakers will monitor their child's symptoms daily with AKL-X01

Objectives:

Primary: To understand the synergistic effects of combining AKL-T01 (with AKL-X01 symptom tracking) as adjunctive treatment to stimulant medication on impairment.

To understand the effects of AKL-T01 (with AKL-X01 symptom tracking) treatment in participants not recently on stimulant medication on impairment.

Secondary: To understand symptom and attentional effects of AKL-T01 (with AKL-X01 symptom tracking) in all participants (both Cohort 1 and Cohort 2).

Exploratory: To understand sustained benefits, through reduction of ADHD impairment and symptoms, following one month of AKL-T01 treatment (with AKL-X01 symptom tracking).

Endpoints:

Primary (Cohort 1, Cohort 2):

- 1) Overall change in clinician-reported Impairment Rating Scale (IRS) "Overall severity of child's problem in functioning and overall need for treatment" score from baseline to Day 28.

Secondary (Cohort 1, Cohort 2):

- 1) Overall change in ADHD-Rating Scale (ADHD-RS) total component score from baseline to Day 28.
- 2) Clinical Global Impression-Improvement (CGI-I) score at Day 28.
- 3) Overall change in Test of Variable Attention-Version 9 (TOVA) attention composite score (ACS) and certain constituent scores, from baseline to Day 28 (the specific constituent scores will be described in the SAP).

Exploratory (Cohort 1, Cohort 2):

- 1) Overall change in clinician-reported IRS "Overall severity of child's problem in functioning and overall need for treatment" score from baseline to Day 56 and from baseline to Day 84.
- 2) Overall change in ADHD-RS total component score from baseline to Day 56 and from baseline to Day 84.
- 3) CGI-I score at Day 56 and at Day 84.
- 4) Overall improvement in TOVA ACS and certain constituent scores, from baseline to Day 56 and from baseline to Day 84.
- 5) Overall change in Test of Silent Reading Efficiency and Comprehension (ToSREC) from baseline to Day 28 and from baseline to Day 84, using the appropriate ToSREC form.
- 6) Overall change in Mathematics Fluency and Calculation Tests (MFaCTs) from baseline to Day 28 and from baseline to Day 84, using the appropriate MFaCTs form.

Descriptive (Cohort 1, Cohort 2):

- 1) AKL-X01 usage, as compared to the expected usage of 5 days per week.

- 2) Participant/Caregiver experience and preference questionnaires.
- 3) Participant demographics.
- 4) Reported adverse events.
- 5) Change in participant's medications.
- 6) Constituent measures of the IRS (individual questions), ADHD-RS (subscales and individual questions), and TOVA.

Study Population:

This study will enroll 203 male and female participants; ages 8 years 0 months to 14 years 9 months, inclusive; with a confirmed diagnosis of attention deficit hyperactivity disorder (ADHD), primary inattentive or combined, per the Mini-International Neuropsychiatric Interview for Children and Adolescents; Diagnostic and Statistical Manual-V. Participants must currently be experiencing sub-optimal treatment of ADHD, based upon results of the CGI-S score, and have an IRS (Parent Report) score of ≥ 3 . Participants must also have an estimated IQ score of ≥ 80 , as assessed by the KBIT. If the participant is to be enrolled into Cohort 1 (stimulant), he/she must be consistently (i.e. stable without changes in dosing) on stimulant medication, at an approved FDA dose, for ≥ 30 days prior to enrollment and in the investigator's opinion, it is acceptable to remain on the same dose throughout the study. If the participant is to be enrolled into Cohort 2 (non-stimulant), he/she must be consistently (i.e. stable without starting and stopping medication) off stimulant medication for ≥ 30 days prior to enrollment and in the investigator's opinion, it is acceptable to remain off of stimulants throughout the study. All participants located within the continental United States.

Potential participants currently experiencing controlled (requiring a restricted medication) or uncontrolled, comorbid psychiatric diagnosis, based on MINI-KID and subsequent clinical interviews, with significant symptoms including but not limited to the following should be excluded from enrollment: post-traumatic stress disorder, psychosis, bipolar illness, autism spectrum disorder, severe obsessive-compulsive

disorder, severe depressive disorder, severe anxiety disorder, conduct disorder, or other symptomatic manifestations that in the opinion of the Investigator may confound study data/assessments. Potential participants who are currently treated with a non-stimulant medication for ADHD (i.e., atomoxetine, clonidine, guanfacine), or who have been diagnosed with ADHD Hyperactive-Impulsive subtype (based upon score on the MINI-KID interview) will be excluded from study participation. Also, any potential participant showing no room for improvement, or those refractory to previously well-administered ADHD treatment, should be excluded.

Description of Sites/Facilities Enrolling Participants:

Approximately 15 sites (mix of institutional sites and private practice centers) located within the continental United States

Study Duration:

[figure not shown]
Approximately 13 months.

Participant Duration:

Approximately 3-4 months.

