4 STUDY DESIGN

4.1 OVERALL DESIGN

This study is a multi-center, open label trial to determine the effect of AKL-T01 treatment (with AKL-X01 mobile app-based symptom tracking) on ADHD symptoms and impairments in children currently on or off stimulant.

Two hundred and three participants (203) at multiple sites will be enrolled into 2 cohorts. 130 participants will be recruited into cohort 1 and 73 participants will be recruited into cohort 2.

Cohort 1 will have been stable** on stimulant(s) for at least 30 days before baseline. At screening (at least 7 and up to 30 days before baseline), participant caregivers will be instructed to download AKL-X01 on to their smartphone. Caregivers will use AKL-X01 for tracking participants' symptoms and behaviors beginning between days -30 and -7, through day 84. During Treatment Phase 1, Days 1 through 28, participants will continue receiving stimulant and will also receive AKL-T01 treatment. During the 1-month treatment pause, Days 29 through 56, participants will continue receiving stimulant but will discontinue AKL-T01. During Treatment Phase 2, Days 57 through 84, participants will continue receiving stimulant and will also receive AKL-T01 treatment.

****Note:** Medication stability is defined as:

- Moderate response on stimulant, but still room for improvement
- Dose unchanged within past 30 days, but other doses have been tried previously without improvement
- Currently taking stimulant, but parent and/or caregiver wishes not to increase dosage for any reason
- Taking consistent stimulant dose on weekdays, but not on weekends

The hypothesis for Cohort 1 is that children receiving stimulant plus AKL-T01 treatment will improve in ADHD symptoms and impairments from Day 0 to Day 28.

Cohort 2 will have been stable without any stimulant for ≥ 30 days before baseline. At screening (at least 7 and up to 30 days before baseline), participant caregivers will be instructed to download AKL-X01 on to their smartphone. Caregivers will use AKL-X01 for tracking participant symptoms and behaviors beginning between days -30 and -7, through day 84. During Treatment Phase 1, Days 1 through 28, participants will receive AKL-T01 treatment. During the 1-month treatment pause, Days 29 through 56, participants will discontinue AKL-T01. During Treatment Phase 2, Days 57 through 84, participants will receive AKL-T01 treatment.

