9 STATISTICAL CONSIDERATIONS

This section provides a brief overview of the statistical analyses, both quantitative and qualitative in nature that will be used during this study. In addition to what follows in this section, further details will be provided in a separate statistical analysis plan (SAP).

The primary objectives of this study are to (1) understand the synergistic impairment effects when combining AKL-T01 (with app-based symptom tracking, AKL-X01) as adjunctive treatment to stimulant medication, and (2) understand the impairment effects of AKL-T01 (with app-based symptom tracking, AKL-X01) treatment in participants not recently on stimulant medication. Within both the medicated and non-medicated cohorts, a change in Impairment Rating Scale (IRS) (Clinician Report) from baseline to Day 28 will demonstrate the overall effect that AKL-T01 treatment has on ADHD symptoms.

The secondary objective of this study is to understand the symptom and attentional effects of AKL-T01 (with app-based symptom tracking AKL-X01) treatment in all participants. There is an additional exploratory objective which focuses specifically on sustained benefits, through reduction of ADHD symptoms and impairment, experienced by participants following (a) 1-month of treatment with AKL-T01, and (b) an additional 4 weeks of AKL-T01 treatment.

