9.1 STATISTICAL HYPOTHESES

The aim of the primary objective is to demonstrate a statistically significant difference on mean change in IRS “Overall severity of child’s problem in functioning and overall need for treatment” score, defined for each participant as the score measured on Day 28 minus the score measured at the baseline visit. In both the medicated and non-medicated cohorts, the statistical significance of the primary efficacy analysis will be assessed using a 2-sided paired *t*-test evaluated at the 95% level of confidence. The formulation of the null (H_0) and alternative (H_a) hypotheses are stated below, where μ_d refers to the true mean difference:

- $H_0: \mu_d = 0$
- $H_a: \mu_d \neq 0$.

If, within a particular cohort, the upper bound of the 95% confidence interval around the sample difference is smaller than 0, we will have sufficient evidence to reject H_0 and conclude that AKL-T01 plus Fengo improves ADHD symptoms in that cohort.

If the set of sample differences is non-normal, defined here as skewness larger than 1.5 in magnitude, the efficacy analysis will proceed as a non-parametric Wilcoxon signed rank test. Significance will be determined by evaluating the *W*-statistic at the 95% level of confidence.

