9.4.9 EXPLORATORY ANALYSES

The following exploratory analysis endpoints will be investigated and descriptive statistics will be summarized in the medicated and non-medicated cohorts using the ITT population:

- 1) Overall change in clinician-reported IRS “Overall severity of child’s problem in functioning and overall need for treatment” score from baseline to Day 56 and from baseline to Day 84.
- 2) Overall change in ADHD-RS total component score from baseline to Day 56 and from baseline to Day 84.
- 3) CGI-I score at Day 56 and at Day 84.
- 4) Overall improvement in TOVA ACS and certain constituent scores, from baseline to Day 56 and from baseline to Day 84.
- 5) Overall change in Test of Silent Reading Efficiency and Comprehension (ToSREC) from baseline to Day 28 and from baseline to Day 84, using the appropriate ToSREC form.
- 6) Overall change in Mathematics Fluency and Calculation Tests (MFaCTs) from baseline to Day 28 and from baseline to Day 84, using the appropriate MFaCTs form.

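### Section 9.1 credits the Day 28 change to AKL-T01 plus Fengo, but Fengo is in planned use at both ends of every change score, so no contrast isolates its effect or estimates the package

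*Combined protocol and SAP*

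**What the plan says.** **Timing of Fengo.** The Synopsis (1.1) starts caregiver tracking early: "For both cohorts, at least 7 and up to 30 days before baseline". Section 4.1 gives its span as "beginning between days -30 and -7, through day 84". In the break between treatment phases only AKL-T01 stops; for Fengo, "during this time caretakers will continue to monitor their child's symptoms daily with AKL-X01". The schedule (1.3) has the app set up at Screening and has staff check at Baseline that the caregiver is entering data.

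**Status of Fengo.** The Synopsis names AKL-T01 as the intervention. It lists Fengo separately, as a tracking aid for caregivers, and adds that "it is not an investigational medical device".

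**The contrasts.** The primary endpoint is the clinician IRS change, "defined for each participant as the score measured on Day 28 minus the score measured at the baseline visit". Section 9.4.9 adds changes in the "score from baseline to Day 56 and from baseline to Day 84". Section 9.4.3 uses baseline to Day 28 for ADHD-RS and TOVA.

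**The conclusion.** Section 9.1 says that an upper 95% confidence limit below zero allows the trial to "conclude that AKL-T01 plus Fengo improves ADHD symptoms in that cohort". The opening of section 9 says that the same change "will demonstrate the overall effect that AKL-T01 treatment has on ADHD symptoms". The section 3 justification column and the section 4.1 hypotheses also speak of AKL-T01 (with stimulant in Cohort 1). Section 9.4.2 repeats the confidence-limit rule but concludes only that the cohort reached significance; it does not mention Fengo.

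**The concern.** The sentence in 9.1 that turns the primary test into a conclusion names two components. One of them, Fengo, is already running when the first clinician IRS, ADHD-RS and TOVA are taken, and it is still running at every later assessment. A change score between two on-Fengo visits is not a comparison of the package with its absence, and it is not a comparison of Fengo with no Fengo.

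What is at stake is the claim, not the test. Followed literally, 9.1 would let a significant result be reported as a benefit of a combination whose effect the contrast does not estimate. The question is separate from whether the IRS measures symptoms or impairment; it would remain if that word in 9.1 were changed.

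**Working it through.** **1. Exposure at each assessment** (1.1, 1.3, 4.1; days on Fengo are the 7- to 30-day lead-in plus the study day)

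| Visit | AKL-T01 | Days since Fengo start | Clinician IRS, ADHD-RS, TOVA |
|---|---|---|---|
| Screening | none | being set up | not taken |
| Baseline | not yet started | 7 to 30 | taken |
| Day 28 | end of first phase | 35 to 58 | taken |
| Day 56 | end of break | 63 to 86 | taken |
| Day 84 | end of second phase | 91 to 114 | taken |

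AKL-T01 goes on and off; Fengo does not. No Fengo-free arm or period is described. The one outcome scale scheduled at Screening is the parent-report IRS, repeated at Day 84. No analysis of its change is listed, and a minimum score on it is an entry criterion (5.1).

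**2. How Fengo time divides around baseline**

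- Shortest lead-in: 7/(7 + 28) = 20% of Fengo time by Day 28 precedes baseline.
- Longest lead-in: 30/(30 + 28) = 52%.
- If the schedule's screening window (ending at Day -8) governs instead, the minimum is 8/(8 + 28) = 22%.

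The remaining 48% to 80% falls after baseline. These are calendar shares; expected use is 5 days per week.

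**3. What the change contains.** Let T be the effect of AKL-T01, F the total effect of Fengo, and s the share of F that arises after baseline. Take the effects as additive and set aside time and regression to the mean. Then:

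- expected Day 28 change = -(T + sF)
- package effect = T + F, which the change equals only if F = 0 or s = 1
- AKL-T01 effect = T, which the change equals only if F = 0 or s = 0

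The design does not identify F or s.

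**4. The plan's own figures (9.2).** n = ((1.960 + 1.2816) × SD/difference)². With SD 1 and 0.30 this is 116.75, so 117. With 0.40 it is 65.67, so 66. Both reproduce. Exact noncentral-t power at those sizes is 89.6% and 89.3%. Nothing here turns on the sample size.

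**5. Illustration.** The documents give no Fengo effect, so F = 0.30 SD is an assumption and s is varied over its full range. The chance that the 9.1 rule is met is 1 - G(t), where t is the 0.975 point of the t distribution on n - 1 degrees of freedom and G is the noncentral-t distribution function with noncentrality (T + sF)√n.

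With T = 0 and F = 0.30:

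| s | T + sF | Cohort 1, n = 117 | Cohort 2, n = 66 |
|---|---|---|---|
| 0 | 0 | 2.5% | 2.5% |
| 0.25 | 0.075 | 12.4% | 8.7% |
| 0.5 | 0.15 | 36.3% | 22.4% |
| 1 | 0.30 | 89.6% | 67.0% |

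With T = 0.30 and s = 0 in Cohort 1, the chance is 89.6% whether F is 0 or 0.30. So the rule can be blind to Fengo or driven by it, depending on a quantity that the trial does not observe.

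**The case against.** Four points on the other side deserve weight.

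- **The phrase in 9.1 may be shorthand.** The objectives repeatedly attach a parenthesis about AKL-X01 tracking to AKL-T01, so adding Fengo in 9.1 may mean only that AKL-T01 is given with the tracker running. This stands as a possible reading, and it is the one the plan should state. A reader might infer that 9.1 and section 3 are irreconcilable. The documents do not support that: section 3 does not exclude the tracker, and no section claims that Fengo itself helps. What remains is one test labelled in two ways.
- **Fengo is not absent from the contrast.** A reader might infer that, because Fengo starts before baseline, its effect cancels from every change score. That goes too far. Each contrast spans 28 to 84 further days of tracking, so any continuing or cumulative effect is inside the change. Only an effect already present at baseline is excluded.
- **The lead-in is sensible.** Starting the tracker early and holding it constant keeps its onset effect out of the AKL-T01 change, which suits the aim in 4.1. This stands; the fault is in the conclusion, not in the lead-in.
- **Section 9.4.2 gives the rule without Fengo.** This stands, and it confines the problem to the wording in 9.1. It does not remove that wording, which is the only place where the hypothesis test is turned into a substantive claim.

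The lack of a concurrent control is a larger limit on causal inference, but it is a separate matter and this correction does not depend on it.

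**Conclusion.** The point holds in this form: the conclusion in 9.1, read literally, credits a combination whose effect no planned contrast estimates, and the same change is worded as an effect of AKL-T01 in sections 3, 4.1 and 9. It applies to both cohorts, all 203 planned participants, and every change from baseline to Day 28, 56 or 84.

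No bias can be sized from the documents. The probabilities in the working rest on an assumed Fengo effect of 0.30 SD, additive effects, and no time trend or regression to the mean. They show only that the result could range from unaffected by Fengo to largely produced by it. The paired comparison remains a valid estimate of change over the 28 days; the claim attached to it needs correcting.

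**What to change.** In 9.1, replace the conclusion with one about the change from baseline over 28 days of AKL-T01 treatment on a background of continuing Fengo use, in that cohort. Make the objectives and justifications in 1.1, 3 and 9 consistent with it, so that the parenthesis about symptom tracking is clearly a background condition. Add one sentence stating that no benefit will be claimed for Fengo, or for AKL-T01 and Fengo as a package, from these endpoints.

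The cost is an edit to the wording and a narrower claim. No test, endpoint, population or sample size changes. Reporting the length of the Fengo lead-in by cohort is optional, because section 9.4.5 already tabulates actual AKL-X01 usage.

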1.2 SCHEMA

The AKIL-05 study design schematic can be found on the following page.

1.3 SCHEDULE OF ACTIVITIES

	Screening	Baseline	Treatment Phase 1		1-Month Break		Treatment Phase 2	
	Days -30 to -8**	Day 0**	Days 1 to 28	Day 28**	Days 29 to 56	Day 56**	Days 57 to 84	Day 84**
Informed consent and assent	X							
Demographics	X							
Medical history/visual acuity testing	X							
Review inclusion/exclusion criteria	X	X						
Enrollment		X						
MINI-KID (administered by trained clinician)	X							
KBIT	X							
Ishihara Color Blindness Test	X							
C-SSRS	X							X
Concomitant medication review	X	X		X		X		X
Configure Fengo on caregiver's phone	X							
Caregiver tracks child's symptoms via Fengo	X	X	X		X		X	
Verify child's caretaker is using HSC (i.e. Parent shows study staff recent data entries on their phone)		X		X		X		X

	Screening	Baseline	Treatment Phase 1		1-Month Break		Treatment Phase 2	
	Days -30 to -8**	Day 0**	Days 1 to 28	Day 28**	Days 29 to 56	Day 56**	Days 57 to 84	Day 84**
Cohort 1: Confirm stimulant dosage		X	X		X		X	
IRS (Clinician Report) (administered by trained clinician)		X		X		X		X
IRS (Parent Report)	X							X
ADHD-RS (administered by trained clinician)		X		X		X		X
CGI-S		X						
CGI-I				X		X		X
TOVA-9		X		X		X		X
ToSREC		X		X		X		X
MFaCTs		X		X		X		X
Complete Experience & Preference Questionnaires								X
Administer AKL- T01 treatment on iPad-Mini and charger ***			X				X	
Collect the iPad-Mini				X				X
Adverse events		X	X	X	X	X	X	X
Caregiver can optionally consent to participate in a 30 to 45 min phone interview (game feature preference discussion) with Sponsor's game designers								X

****Note: All study visits for each participant should be completed during the same time of day (either AM or PM), to maintain consistent data collection and comparison of rater assessment results.**

*****If the iPad and charger are not returned to the site within 7 days of visit Day 28 and Day 84, it will be noted as a protocol deviation**

Conditions of Obtaining Assent vs Consent:

Visits at Day 28, Day 56 and Day 84 are allowed a window of +/-3 days, calculated based upon Baseline Visit date. (The participant should be encouraged to continue their AKL-T01 treatment during this exception period for Day 28 and Day 84 visits).

